## 5.3 EXCLUSION CRITERIA

- 5.3.1 Patients with contraindication for cardiac surgery;
- 5.3.2 Patients who are pregnant.
  - 5.3.2.1 Pregnancy will be assessed by patients informing the physicians.
- 5.3.3 Patient is unwilling to or has an inability that reduces his mobility in order to attend the required follow-up visits.
- 5.3.4 Patient has active endocarditis (patients with previous endocarditis must have two documented negative blood culture results prior to enrollment).
- 5.3.5 Patient has had an acute preoperative neurological event defined as patient has not returned to baseline 30 days prior to the planned valve implantation surgery.
- 5.3.6 Patient is undergoing renal dialysis.
- 5.3.7 Patient has a documented history of substance abuse within one year of enrollment or is currently a prison inmate.
- 5.3.8 Patient has a documented thrombus in left atrium or left ventricle.
- 5.3.9 Patient had in the past mitral or tricuspid valve replacement.
- 5.3.10 Patient needs mitral and/or tricuspid valve replacement.
- 5.3.11 Patient has an Ejection Fraction < 25%
- 5.3.12 Patient had the Trifecta™ valve implanted as part of this study, but then had the device explanted (a patient cannot be enrolled twice in this study).
- 5.3.13 Preoperative evaluation indicates other significant cardiovascular abnormalities such as aortic dissection or ventricular aneurysm.
- 5.3.14 Patient has a life expectancy less than two years.

## **6 INVESTIGATION DESIGN**

### **6.1 TYPE**

This investigation is a multicenter, prospective, observational study.

[figure not shown]
### **6.2 DURATION**

- 6.2.1 The first enrollment is anticipated in 2010.
- 6.2.2 The enrollment period will be approximately 15 months.
- 6.2.3 The patient will participate in this investigation for approximately 10 years from enrollment to the last follow-up.
- 6.2.4 The patient may withdraw from the investigation at any time, for any reason. In this case, the procedures for reporting should be followed as mentioned in the section 0 Early Conclusion to Patient Participation.

### **6.3 ENROLLMENT TARGET**

- 6.3.1 The enrollment target for this investigation is 801 patients. For more information, refer to section 8.1 Sample Size Justification.

### **6.4 DESIGN**

## 7 PRODUCT

The following market approved St. Jude Medical products are required to be used in the investigation:

### 7.1.1 The Trifecta valve:

The Trifecta valve is a tri-leaflet stented pericardial valve designed for supra-annular placement in the aortic position. The valve is fabricated using a polyester-covered titanium stent. The stent, excluding the sewing cuff, is then covered with porcine pericardial tissue. This covering minimizes mechanical wear by allowing only tissue-to-tissue contact during valve function. A silicone insert within the polyester sewing cuff is contoured to conform to the shape of the native annulus. The valve leaflets are fabricated from bovine pericardium. The porcine and bovine pericardium are preserved and crosslinked in glutaraldehyde. Glutaraldehyde, formaldehyde, and ethanol are used in the valve sterilization process. The Trifecta valve is processed using Linx™ anti-calcification technology. The Trifecta valve received CE mark in March 2010.

### 7.1.2 Trifecta Sizer Set TF2000:

The Trifecta™ Sizer Set Model TF2000 is a double-ended tool with a cylindrical annular sizing end and a valve replica end. The cylindrical annular sizing end of the sizer is used to determine the size of the annulus. The replica end of the sizer is used to visualize placement of the sewing cuff above the annulus and to confirm placement and fit of the valve in the supra annular space. Both the cylindrical sizing head and the valve replica head are connected to the sizer handle via a bendable section that allows for easier access to the aortic anatomy. The UT2000 Holder Handle interfaces with the Trifecta valve holder via a click-in mechanism. The holder handle is used to transport the valve from the jar and through the valve rinse procedure. In addition, the holder handle helps to facilitate valve suturing and delivery of the valve into the implant position.

## **8 STATISTICAL ANALYSIS PLAN**

### **8.1 SAMPLE SIZE JUSTIFICATION**

- 8.1.1 The sample size estimation is based on the primary endpoint of this study, freedom from reoperation due to SVD at year 10 post implant for patients who have the Trifecta valve implanted.
- 8.1.2 It is assumed that the expected freedom rate from reoperation due to SVD at year 10 post implant will be  $96.5\% \pm 1.52\%$ , in order to establish a one side 95% confidence interval for the freedom rate with the lower bound as 94%, the required number of patients at risk at year 10 post implant is at least 142 using non-parametric survival analysis with Peto's variance. Assuming the overall mortality rate will be 39.50% at year 5 and 63.4% at year 10, the minimum sample size is 641 patients.
- 8.1.3 With 20% drop out rate, in total at least 801 patients need to be recruited.
- 8.1.4 Taking into account the effect of learning curve of the surgeons, the first 3 patients implanted by each surgeon without any experience with the Trifecta valve are not counted as part of the sample size.

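### The sample sizes of 641 and 801 do not follow from the stated mortality: 5-year and 10-year survival are multiplied together, so deaths in years 0-5 are removed twice, or 63.4% is mislabelled

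*Combined protocol and SAP*

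**What the plan says.** Section 8.1.2 sizes the study for precision. Expected 10-year freedom from reoperation for SVD is 96.5%, with 1.52% attached to it, and the one-sided 95% lower bound should be 94%. From this, "the required number of patients at risk at year 10 post implant is at least 142". The next sentence allows for deaths: "Assuming the overall mortality rate will be 39.50% at year 5 and 63.4% at year 10, the minimum sample size is 641 patients". Section 8.1.3 then allows for drop-out: "With 20% drop out rate, in total at least 801 patients need to be recruited". Section 6.3.1 carries the result forward: "The enrollment target for this investigation is 801 patients". Section 8.1.4 sets some patients aside: "the first 3 patients implanted by each surgeon without any experience with the Trifecta valve are not counted as part of the sample size".

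The plan shows no formula for the step from 142 to 641 and names no source for the two mortality figures. It does not say anywhere that 63.4% applies only to patients alive at year 5.

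**The concern.** A mortality figure attached to year 10 and described as overall is naturally read as cumulative from implant, so survival to year 10 is 1 - 0.634 = 0.366. Only that factor is needed to get from patients recruited to patients alive at year 10. The year-5 figure describes an intermediate point on the same curve and should not enter again. The printed 641 is far larger than this route gives.

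The enrollment target is the figure at stake. The calculation that justifies it contradicts its inputs as labelled, and a reader cannot tell whether the plan assumes 63.4% or 77.9% overall mortality at year 10. That decides whether 801 patients leave a comfortable margin over the 94% criterion or almost none.

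**Working it through.** **Inputs (8.1.2, 8.1.3, 6.3.1).** Freedom S = 0.965; SE = 0.0152, which is (0.965 - 0.94)/1.645; mortality 39.5% at year 5 (survival 0.605) and 63.4% at year 10 (survival 0.366); drop-out 20%; target 801.

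**1. Number at risk.** Peto's variance is S²(1 - S)/n, so n = 0.965² x 0.035/0.0152² = 141.07, rounded up to 142. The plan's figure is reproduced.

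**2. How 641 and 801 arise.**
- 142/(0.605 x 0.366) = 142/0.22143 = 641.29
- 641/0.8 = 801.25

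Other routes miss 641:
- 142/0.605 = 235
- 142/0.366 = 388
- 142/(0.605 x 0.366 x 0.965) = 665
- 142/0.366 with the drop-out factor applied twice = 606

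**3. Which kind of mortality is 63.4%?** 1 - 0.605² = 0.633975, or 63.4%. Two successive 5-year periods at 39.5% each give exactly the year-10 figure, which points to a cumulative rate. On that constant hazard the product used in step 2 is about 0.605³ = 0.2214, which is survival to year 15.

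**4. Reading A: 63.4% is cumulative.**
- Before drop-out: 142/0.366 = 387.98, so 388
- After drop-out: 388/0.8 = 485
- 801/485 = 1.65

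Patients already reoperated for SVD (3.5%) have also left the risk set. The plan does not allow for them; doing so gives 142/(0.366 x 0.965) = 402.05, so 403, and 403/0.8 = 503.75, so 504.

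**5. Reading B: 63.4% is mortality in years 5-10 among 5-year survivors.** The product is then right, and 641 and 801 stand apart from rounding (rounding up at each step gives 642 and 803). Overall 10-year mortality is 1 - 0.605 x 0.366 = 77.9%.

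**6. What 801 recruits give at year 10.** SE = √(0.965² x 0.035/n); lower bound = 96.5% - 1.645 x SE. The smaller count in each range removes SVD reoperations.

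| | Reading A | Reading B |
|---|---|---|
| At risk | 801 x 0.8 x 0.366 = 234.5; x 0.965 = 226.3 | 801 x 0.8 x 0.605 x 0.366 = 141.9; x 0.965 = 136.9 |
| SE | 1.18% to 1.20% | about 1.5% |
| Expected lower bound | 94.56% to 94.53% | about 94.0% |
| Chance that the bound is at least 94% | 0.66 to 0.69 | 0.51 to 0.52 |

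The last row is from simulation: 6,000 runs per setting, true freedom 96.5%, exponential death and drop-out, Weibull SVD times with shapes 1, 3 and 5. These hazard shapes are assumptions, not taken from the plan. Under Reading A, 485 patients give 0.51 to 0.52.

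**7. Learning-curve patients.** Section 8.1.4 does not count them towards the sample size, yet 6.3.1 gives 801 with no allowance for them. The number of surgeons is not given. If, as an assumption, 0, 50, 100 or 150 of the 801 were such patients, Reading A leaves 226, 212, 198 or 184 at risk (SVD reoperations removed), with lower bounds of 94.53%, 94.46%, 94.39% and 94.31%. At 150 the simulated chance is 0.60 to 0.62.

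**The case against.** The word 'overall' may mean all-cause rather than cumulative: the secondary endpoints in 4.2 separate survival from valve-related death. If so, the word does not settle the time base. The product in step 2 is also inferred from the result, since the plan prints no formula, and on Reading B the printed sizes are right. This part stands to the extent that the documents cannot prove which reading was intended. It does not rescue the text. A mortality rate at year 10, paired with one at year 5 under a single noun phrase, reads as cumulative even if it means all-cause, and the identity 1 - 0.605² = 0.634 supports that. On either reading something in 8.1.2 has to change.

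A second objection is that the consequences are small: no patients are added, the decision rule in 8.2.1 is untouched, and the error is conservative if 63.4% is cumulative. That is correct and limits the weight of the point.

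A third is that the plan makes a precision calculation and claims no power, so success probabilities go beyond it, as do the SVD-adjusted sizes and the illustrative 150 learning-curve patients. That is fair. They show the scale of the matter, and the conclusion does not depend on them.

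**Conclusion.** The concern holds and should be fixed. With mortality as labelled, the plan's own method gives 388 before drop-out and 485 after, not 641 and 801; the target is about 65% larger than its stated justification supports. This takes the 142, the 20% drop-out and the division by 0.8 as given, and none of these is disputed. The arithmetic is certain. Cumulative mortality is the more likely meaning, but the documents do not settle it. If it is the meaning, the surplus acts as an undeclared reserve. If the conditional meaning was intended, the sizes are right, the description of 63.4% is wrong, and the study has almost no margin over 94%.

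**What to change.** Rewrite 8.1.2 and 8.1.3 to show the formula and say which mortality is meant.

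- **If 63.4% is overall 10-year mortality:** give 388, and 485 after drop-out (403 and 504 if SVD reoperations are also taken out of the risk set), with the 8.1.4 patients additional. The target of 801 can be kept if it is restated as giving about 226-235 at risk at year 10, an SE of about 1.2% and an expected lower bound of about 94.5%. It would help to add that the chance of meeting 94% is about two thirds if true freedom is 96.5%, naming the hazard assumptions.
- **If 63.4% is mortality in years 5-10 among 5-year survivors:** keep 641 and 801, say so, and give overall 10-year mortality as 77.9%.

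In either case, state in 6.3.1 and 8.1.4 whether the 801 includes the learning-curve patients. The cost is protocol and SAP wording only, with no extra patients or procedures.

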### **8.2 ENDPOINT ANALYSIS**

- 8.2.1 Non-parametric survival analysis will be used to calculate the freedom rate( $S$ ) from reoperation due to SVD at year 10 post implant and the corresponding variance ( $Var_s$ ) will be computed with Peto's formula for survival analysis. The lower bound of the 95% confidence interval for  $S$  will be calculated using the formula  $S - Z_{0.5} * (Var_s)^{1/2}$ . If the lower bound of  $S$  is bigger than or equal to 94%, then the expected estimate is confirmed. The survival time will be calculated as the number of days from implant date to reoperation date due to SVD. A Kaplan-Meier curve with the cumulative survival rate will also be presented.
- 8.2.2 A Cox regression model will be used to further investigate the effects of the factors on the primary endpoint. These factors include baseline factors such as learning curve (1, 2, 3, >3), age, gender, NYHA Class etc..

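### Section 8.2.1 prints the multiplier of the deciding confidence bound as Z(0.5), which is zero, where 8.1.2 requires 1.645; its conclusion should also read at least 94%

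*Combined protocol and SAP*

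**What the plan says.** Section 8.2.1 of the combined protocol and SAP estimates S, the freedom rate at year 10, by non-parametric survival analysis and takes its variance, Var_s, from Peto's formula. It then defines "The lower bound of the 95% confidence interval for" S as S − Z(0.5) × √Var_s, with 0.5 as the subscript in the text as supplied. If that bound "is bigger than or equal to 94%, then the expected estimate is confirmed". The section does not say whether the interval is one- or two-sided, and it does not define the expected estimate.

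Section 8.1.2 gives the planning basis for the same endpoint. It puts the expected rate at 96.5% ± 1.52%. The purpose of the sizing is stated as "in order to establish a one side 95% confidence interval for the freedom rate with the lower bound as 94" (per cent). From these figures the plan derives its requirement: "the required number of patients at risk at year 10 post implant is at least 142". The variance method is the same as in 8.2.1, namely Peto's.

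No other text says when the primary endpoint is met. Section 8.2.2 is a Cox model to explore baseline factors, and 8.3 is descriptive.

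**The concern.** The 50th percentile of the standard normal distribution is 0 under either tail convention. With that multiplier the lower bound has no margin for sampling error, and the rule reduces to asking whether the point estimate is at least 94%. This cannot be a 95% confidence bound, so the formula contradicts its own sentence as well as 8.1.2.

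A second, smaller problem does not depend on the subscript. The only expected rate in the plan is 96.5%, while 94% is the target for the lower bound. A rule that declares the expected estimate confirmed when the bound reaches 94% invites a report that 96.5% was confirmed, when the data would support only a rate of at least 94%.

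At stake is the one sentence that turns ten years of follow-up into a conclusion about durability.

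**Working it through.** **Inputs.** From 8.1.2: expected S = 0.965, target bound 0.94, one-sided 95%, SE 1.52%, 142 at risk at year 10, mortality 39.5% at year 5 and 63.4% at year 10, 641 patients before dropout. From 8.2.1: multiplier Z(0.5), threshold 94%. The plan names Peto's variance without printing it. I take SE = S × √((1 − S)/n), with n the number at risk at year 10.

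**Step 1: reproduce the plan's figures.**
- The distance from expected rate to bound is 96.5 − 94 = 2.5 points. The implied multiplier is 2.5/1.52 = 1.645, the one-sided 95% value.
- Required n = S² × (1 − S) × (z/0.025)². With z = 1.645: 0.965² × 0.035 × (1.645/0.025)² = 141.1, rounded up to 142. This matches the plan.
- SE at n = 142: 0.965 × √(0.035/142) = 1.515%, which agrees with 1.52%.
- Alternatives fail: z = 1.96 gives 200.3, so 201; a binomial variance with 1.645 gives 146.2, so 147. With z = 0 no n follows at all.

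**Step 2: the bound at S = 96.5% and 142 at risk.**

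| Multiplier | Lower bound | Smallest S that passes |
|---|---|---|
| 0 (as printed) | 96.5% | 94.0% |
| 1.645 | 94.01% | 96.49% |

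**Step 3: what the printed rule would do if followed.** By normal approximation at a true rate of 94% and n = 142, the SE is 0.94 × √(0.06/142) = 1.93%.
- z = 0: the pass threshold is 94.0%, so the chance of passing is 50%.
- z = 1.645: (96.49 − 94)/1.93 = 1.29, so the chance is about 10%.

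A simulation gives the same contrast. Its assumptions are:
- 641 patients;
- death as censoring, independent of SVD;
- an SVD hazard that is constant or rising (Weibull shape 3);
- Kaplan-Meier S with Peto variance at year 10;
- 4,000 runs per cell, with Monte Carlo error at most 0.8 points.

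The ranges below cover both hazards and two readings of the mortality figures, which leave about 220–227 or 132–137 at risk at year 10.

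| True 10-year rate | Passes with z = 0 | Passes with z = 1.645 |
|---|---|---|
| 94% | 51–53% | 3–7% |
| 93% | 23–31% | 1–2% |

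The approximation gives 10% rather than 3–7% because it takes Peto's SE as the actual spread of S. The comparison with one half is unaffected.

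**Step 4: the conclusion, using 1.645.** At the planned 142 at risk, the smallest passing estimate is 96.49%, almost exactly the expected 96.5%. If 63.4% is read as cumulative 10-year mortality, 641 × 0.366 = 235 remain at risk (before reoperations), and an estimate of 96.05% passes. The threshold and the expected rate therefore coincide only near 142 and separate as more patients remain at risk.

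**The case against.** The strongest objection is that the subscript may not be an error in the plan. A PDF read by a program can lose a character, and 0.05 in the source would remove the main point. Even if the slip is in the source, the words beside the formula say 95%, 8.1.2 says one-sided, and only 1.645 reproduces the plan's figures. The pass rates at z = 0 describe an analyst who ignores all of this. That stands: the practical harm is small and the check against the source comes first. What remains is that a rule followed as printed gives the wrong answer.

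On the conclusion, the objection is that the two sections fit together. With 1.52% as a standard error, 96.5 − 1.645 × 1.52 = 94.0, so 94% is the lower bound that belongs to the expected estimate, and at 142 at risk passing almost requires an observed 96.5%. The threshold is also explicit, and the estimate will be reported with its curve. This too stands in large part. It makes the point a correction of wording, but does not make the wording right, because the agreement depends on the number at risk.

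A reader might go further in three ways that the documents do not support:
- **96.5% ± 1.52% as a range that excludes 94%.** The arithmetic above shows that 1.52% is a standard error, so there is no such conflict.
- **A pass at a true rate between 94% and 96.5%, such as 96.0%, as a false pass.** The threshold is 94%, so that pass is correct.
- **Sidedness as a contradiction.** Section 8.1.2 states one side for the same endpoint, variance and threshold; 8.2.1 merely omits it.

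Finally, this is an observational study with no stated hypothesis test, alpha or power. The pass rates illustrate the effect of the multiplier and are not the study's declared operating characteristics.

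**Conclusion.** Wrong as written in the supplied text, with little practical harm. The printed multiplier of 0 is incompatible with a 95% bound and with 8.1.2, where the 142 at risk requires 1.645. Followed literally, it would pass a true rate of 94% about half the time instead of 3–7% (about 10% by normal approximation). These rates rest on the simulation assumptions stated, including independent censoring by death. The most likely explanation is a slip for 0.05. If the source reads 0.05, this part falls away.

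The secondary point stands whatever the subscript. A bound of at least 94% supports a rate of at least 94% and does not confirm 96.5%. The gap is negligible at 142 at risk (96.49%) and modest at 235 (96.05%).

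A reader might infer that the sample size is affected. It is not, because 142 was derived with 1.645.

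**What to change.** First check the subscript against the source PDF. Then, in 8.2.1, replace the formula and the clause that a bound which "is bigger than or equal to 94%, then the expected estimate is confirmed" with:

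*Lower limit of the one-sided 95% confidence interval = S − 1.645 × √Var_s. If this limit is at least 94%, 10-year freedom from reoperation due to SVD is concluded to be at least 94%.*

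This also states the sidedness where the analysis is defined. If the source already reads 0.05, stating one-sided and 1.645 is still worthwhile, and the change to the conclusion is still needed. The cost is one formula and one sentence, made before the analysis, with no change to sample size, data collection or conduct.

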### **8.3 ADDITIONAL DATA**

- 8.3.1 For the time to event data, survival analysis will be used to estimate the survival rate and 95% confidence interval, and a Kaplan Meier curve will also be presented.
- 8.3.2 Continuous data will be summarized with mean, standard deviation, median and range. Frequency and percentage will be reported for all categorical data.

---

 Reference : Alan B cantor , SAS survival analysis techniques for medical research

## 9 PROTOCOL DESCRIPTION

### 9.1 PROTOCOL PROCEDURES - OVERVIEW

Table 1 – Protocol Procedure Overview

These activities are applicable to all patients.

(\*) This is only when available

(\*\*) This is **only to be performed when applicable.**

	When	Window	Activities
Pre-Intervention		Not Applicable	
 
• Patient Eligibility
 
• Patient Informed Consent
 
• Patient Demographics & Physical Examination
 
• Patient Cardiovascular History
 
• Patient Current Cardiac Medications
 
• Patient Medical History
 
• Echo (*)
 

Intervention (+baseline)		Not Applicable	
 
• Aortic Valve Replacement Information
 
• Operative Information
 
• Adverse Events(**)
 
• Echo (*)
 

Pre-discharge		Not Applicable	
 
• Patient Current Cardiac Medications
 
• Adverse Events(**)
 
• Echo (*)
 

Yearly follow-up	Yearly	<30 days >61 days	
 
• Patient Current Cardiac Medications
 
• Adverse Events (**)
 
• Echo (*)
 

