#### **4.2 SECONDARY ENDPOINTS**

- 4.2.1 The secondary endpoints of this investigation are:
  - 4.2.1.1 Actuarial survival rate;
  - 4.2.1.2 Freedom from valve related death;
  - 4.2.1.3 Freedom from structural valve deterioration.

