#### 9.2.2 List of Anticipated Adverse Events and Adverse Device Effects:

The following represents a list of anticipated Adverse Events (AE) and Adverse Device Effects (ADE) experienced in either animal and/or clinical studies to date with aortic valve replacement operations, or reported in instructions for use and literature. Anticipated Adverse Events (AE) and Adverse Device Effects (ADE) include: Angina (chest pain), Cardiac arrhythmias, Bleeding events (including pre-operative bleeds), Death (valve and non-valve related), embolism, endocarditis, explant, heart failure, hemolysis, haemolytic anemia, myocardial infarction, non-structural dysfunction, paravalvular leak, valve regurgitation, reoperation, stroke, structural deterioration, valve thrombosis, valvular pannus.

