### 9.2.3 Procedure for Recording and Reporting Adverse Events

- 9.2.3.1 Safety surveillance and reporting will be done for all patients enrolled in the investigation.
- 9.2.3.2 Safety surveillance and reporting starts at the time when the patient is enrolled into the investigation (date of signature of the informed consent) until the last investigational visit has been performed, or the patient has died, or the patient concludes his participation into the study.
  - 9.2.3.2.1 **All Serious Adverse Events and all Adverse Device Effects** are to be documented and reported to the sponsor **immediately**.
  - 9.2.3.2.2 **Non-Serious Adverse Events** documentation and reporting are limited to cardiovascular and neurovascular events.
- 9.2.3.3 Should an AE occur, record AE information in the hospital records, document the information into the Adverse Event case report form (CRF) as soon as possible. By completing the CRF the sponsor will be notified.
  - 9.2.3.3.1 Refer to appendices "Data Collection" and "Data Collection Method".
  - 9.2.3.3.2 Access the eCRF application.
  - 9.2.3.3.3 Select the visit the AE is related to or indicate it as unscheduled visit.
  - 9.2.3.3.4 Enter adverse event information into the **AE Notification** section of the CRF.
    - Date the AE occurred;
    - Date the center investigator or delegate became aware of the AE;
    - Main complaints/symptoms of the AE;
    - Initial diagnosis of the AE;
    - Potential cause of the AE;
    - Pre-existing medical conditions related to the AE;
    - Seriousness of the AE;
    - Device relationship to AE; and
    - Status of the AE.
  - 9.2.3.3.5 The CRF must be authorized by the principal investigator or delegated co-investigator.
  - 9.2.3.3.6 Submit the CRF. When the CRF is submitted, an alert is generated notifying the sponsor.

9.2.3.3.7 As soon as the final details are available for the adverse event, the information should be reported on the AE Follow-Up section of the CRF.

9.2.3.3.8 Access the eCRF application.

9.2.3.3.9 Edit AE CRF, document information into the **AE Follow-Up** section of the case report form.

- Hospitalization details (if applicable);
- Diagnostic test information (if applicable);
- Treatment given (if applicable);
- Final medical diagnosis & cause;
- Patient condition;
- Final AE status;
- Seriousness of AE based on final medical diagnosis and cause;
- Relationship of AE to device based on final medical diagnosis & cause.

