## 9.3 Patient Death

### 9.3.1 Procedure for Recording and Reporting Patient Death

9.3.1.1 Safety surveillance and reporting will be done for all patients enrolled in the investigation.

9.3.1.2 Safety surveillance and reporting starts at the time when the patient is enrolled into the investigation (date of signature of the informed consent) until the last investigational visit has been performed.

9.3.1.2.1 All **Patient Deaths** are to be documented and reported to the sponsor **immediately**.

9.3.1.3 Should death occur, record death information in the hospital records, **immediately** document the information in the Death case report form (CRF). By completing the CRF the sponsor will be notified.

9.3.1.3.1 Refer to appendices "Data Collection" and "Data Collection Method".

9.3.1.3.2 Access the eCRF application.

9.3.1.3.3 Select the visit the patient death is related to or indicate it as visit unscheduled visit.

9.3.1.3.4 Enter patient death information into the Patient Death CRF.

- Date the death occurred;
- Date the center investigator or delegate became aware of the death;
- Place where death occurred (e.g. hospital, nursing home, patient's home);
- If death was witnessed;
- If autopsy was performed;
- If the Trifecta Valve was returned to SJM? If not, reason should be specified.
- Temporal cause of death
- Primary cause of death including if death was caused by valve-related complications (hemolysis, bleeding event, structural valve deterioration, endocarditis, non-structural dysfunction, valve reoperation, embolism, sudden unexplained, valve thrombosis)
- Details regarding death; and
- If details of serious adverse event associated to the death are known by the center/investigator/delegate.

9.3.1.3.5 The CRF must be authorized by the principal investigator or delegated co-investigator.

9.3.1.3.6 Submit the CRF. When the CRF is submitted, an alert is generated notifying the sponsor.

- 9.3.1.4 Patient death may be an outcome of a serious adverse event (SAE). If the death is related to a SAE, all the efforts to get SAE details should be made and the Adverse Event CRF must be completed.
- 9.3.1.5 Patient death is an early conclusion to the patient's participation in the investigation. Complete Termination CRF.
- 9.3.1.6 The investigator must notify the EC or IRB, if appropriate, in accordance with national and local laws and regulations.

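### Does freedom from structural valve deterioration (SVD) need its own event-date and censoring rule, given that echo is optional?

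*Combined protocol and SAP*

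**What the plan says.** Section 4.2.1.3 lists "Freedom from structural valve deterioration" as the third secondary endpoint. The only definition of survival time is in section 8.2.1, and it serves the primary endpoint: "The survival time will be calculated as the number of days from implant date to reoperation date due to SVD". Everything else comes under section 8.3.1: "For the time to event data, survival analysis will be used to estimate the survival rate and 95% confidence interval", with a Kaplan-Meier curve.

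On ascertainment, Table 1 in section 9.1 marks echo at every visit with the footnote "This is only when available". Section 9.9.3.3 repeats the condition for yearly follow-up, and section 9.9.1 allows the yearly contact to be by telephone.

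On recorded dates, the adverse event form holds "Date the AE occurred" (9.2.3.3.4). The Death form holds the date and primary cause of death, with causes that include "structural valve deterioration, endocarditis, non-structural dysfunction" (9.3.1.3.4). The Termination form holds the exit date (9.4.3.4).

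Explant is foreseen. It is in the list of anticipated events ("embolism, endocarditis, explant, heart failure", 9.2.2), and section 5.3.12 bars re-enrolment of a patient who received the valve in the study "but then had the device explanted (a patient cannot be enrolled twice in this study".

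**The concern.** Two things look wrong.

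First, no sentence turns the recorded dates into an event or censoring time for freedom from SVD. If patients are followed to last contact, a valve that was never imaged counts as free of SVD unless the deterioration surfaces through an adverse event, a reoperation or a death. With optional echo and telephone visits, the curve could be too high, and a reader could not tell by how much without knowing how many valves were scanned each year.

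Second, explant is not among the reasons for early conclusion in section 9.4.2, and section 9.4.1 asks sites to keep patients in the study. A patient whose valve was removed for another reason, such as endocarditis, could therefore stay at risk of deterioration in a valve no longer there.

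The primary objective is long-term durability, and this is the listed endpoint that can show deterioration before or without reoperation. An optimistic estimate would flatter the valve.

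**Working it through.** **The plan's own figures.** None is given for freedom from SVD. The sample size belongs to the primary endpoint. With S = 0.965, bound L = 0.94 and one-sided z = 1.645, Peto's variance gives n = S²(1−S)·[z/(S−L)]² = 141.1, so 142 at risk. Then 142/(0.605 × 0.366) = 641.3 and 641/0.80 = 801.25, matching the stated 641 and 801. Nothing below alters these numbers.

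**What an analyst would do by default.**

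| Question | Where the data are | Ordinary choice |
|---|---|---|
| SVD seen on echo or reported as an event | Echo data in the visit window (9.9.3.3); adverse event date (9.2.3.3.4) | Event at earliest evidence |
| Reoperation for SVD | Implant-to-reoperation time (8.2.1) | Event |
| Death with SVD as cause | Death form (9.3.1.3.4) | Event |
| Death from another cause; exit | Death form; Termination form (9.4.3.4) | Censor |
| Valve removed for another reason | Explant as anticipated event (9.2.2), dated on the adverse event form | Censor, since the valve is gone |
| None of these | Yearly contact (9.9.1) | Censor at last contact |

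Every row can be filled from what the protocol says is collected.

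**Optimism from missing echo (assumed inputs).** Assume true 10-year freedom of 90%, echo at each of years 1 to 10 with probability p unrelated to valve status, no other route of detection, and death unrelated to SVD. Kaplan-Meier censored at death then estimates the distribution of detection time, so the plan's 63.4% ten-year mortality affects precision only. With F the distribution of onset time,

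apparent freedom = 0.90 + Σ [F(k) − F(k−1)]·(1−p)^(11−k), k = 1 to 10.

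For rising risk (Weibull shape 3) and p = 0.7, F(10), F(9), F(8), F(7), F(6) = 0.1000, 0.0739, 0.0525, 0.0355, 0.0225. The missed share is 0.0261 × 0.3 + 0.0214 × 0.09 + 0.0170 × 0.027 + 0.0130 × 0.0081 ≈ 0.0103, so the curve reads 91.0%.

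| Yearly coverage | Shape 3 | Constant hazard |
|---|---|---|
| 90% | 90.3% | 90.1% |
| 70% | 91.0% | 90.4% |
| 50% | 92.2% | 91.0% |
| 30% | 94.0% | 92.2% |

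If SVD also surfaces clinically at 0.15 per year after onset (simulation, shape 3), the column reads 90.3, 90.9, 91.9 and 93.3%. At 0.5 per year the bias at 70, 50 and 30% coverage falls to 0.7, 1.4 and 2.2 points. For comparison, the sampling SD of Kaplan-Meier in simulated studies of 801 patients with 20% drop-out is 1.6 points at 70% coverage and 1.4 at 30%.

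**Explant left at risk (assumed rates).** With constant hazards, λ = −ln(0.90)/10 = 0.0105 and explant hazard e, let a(t) = exp[−(λ+e)t] and b(t) = [e/(λ+e)]·[1−a(t)]. Apparent freedom is exp[−∫λ·a/(a+b)dt]. Ten-year explant risks of 2, 5 and 10% give 90.1, 90.3 and 90.5%. With shape 3 the excess is 0.3 to 0.4 points at 0.5% per year and 0.6 to 0.8 at 1% per year.

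**What a written rule would change.** A rule that still censors at last contact reproduces the table above exactly, so it does not remove the optimism. A yearly coverage table describes the problem but alters no estimate. An interval-censored (Turnbull) estimate does alter it, but not reliably for the better. In simulation with true freedom of 90%, if echo is done in 30% of patients without SVD and 70% with it, Kaplan-Meier gives 91.0% and Turnbull 85.1%. At 10% and 50%, they give 92.2% and 74.8%. Turnbull is also less precise (SD 2.3 against 1.6 points at 50% coverage).

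**The case for a change.** The strongest reply is that silence leaves a choice open until the data are seen. Censoring at last contact and censoring at last echo give different curves, the plan permits both, and a sentence would settle it at almost no cost. At 30% coverage the assumed bias of 2.2 to 4.0 points exceeds the SD of 1.4, so it need not be small. Nor does the guideline cited in section 9.2.1.2.1 settle the matter within the plan: it is cited there for event definitions, and no passage turns it into an event-date or censoring rule.

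Most of that is fair. The omission is genuine, it extends to censoring for the primary endpoint in section 8.2.1, and showing echo coverage beside the estimate would be good reporting. What does not follow is that the plan yields a wrong result that a rule would correct. SVD is an anticipated, dated adverse event, and section 9.9.5.1 has sites ask about events at each follow-up, so echo is not the only route to detection. A hastily written rule can also do harm: censoring at every death would discard deaths that the Death form attributes to SVD, which pushes the estimate upward.

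**Conclusion.** The concern is correct as a description of what section 8 leaves out, but it does not call for a change. The missing rule is one that analysts fill sensibly from dates the protocol already collects, including censoring at removal of the valve for another reason. The optimism from unscanned valves comes from optional echo, an accepted trade-off in an observational study, and wording in section 8 cannot remove it.

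Its size rests wholly on assumptions. With 90% true freedom and echo-only detection, it is 0.4 to 1.0 points at 70% coverage (below one sampling SD) and 2.2 to 4.0 points at 30%. It is smaller if SVD also surfaces clinically. It could be larger if patients with SVD are scanned less often or die sooner: with the death hazard doubled after SVD and 50% coverage, Kaplan-Meier gives 92.9% rather than 92.2%. The explant effect is below one point at the rates tried. Freedom from SVD is secondary with no threshold or decision attached, and the sample size and the dated primary event are not directly affected. The published estimate should be read with the echo coverage in view.
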